**Interpretation and limitations.** Based on prior animal studies we anticipate that the high fat diet will modify the composition of the intestinal microbiota towards an unfavorable microbiome profile. Specifically, we anticipate that there will be a reduction in Bifidobacteria content (22). Since Bifidobacteria protect the integrity of the intestinal barrier (24, 39) we expect that the high fat diet will enhance intestinal permeability, which will lead to increased plasma LPS concentration. If our hypothesis is correct, the elevation in LPS will trigger an inflammatory response in muscle, manifested by increased flux through TLR4 (TLR4-MyD88 association, activation of IKK/NF $\kappa$ B and MAPK). We predict that TLR4 stimulation will result in impaired insulin signaling (enhanced IRS-1 ser phosphorylation and decreased IRS-1 tyr phosphorylation, PI 3-kinase activity, and Akt-AS160 phosphorylation) and reduced peripheral insulin sensitivity (low Rd) during the clamp. Based on studies in rodents (24, 39), we predict that the synbiotic will ameliorate the damage to the intestinal epithelium (*i.e.* permeability) and the rise in plasma LPS caused by the high fat diet, which in turn will blunt the inflammatory response (TLR4 signaling) and improve insulin resistance.

In this Aim the effect of the LPS-binding agent sevelamer also will be assessed to provide an independent way for reducing plasma LPS concentration. Based on previous human studies (35, 36) and our preliminary studies (Fig. 11) demonstrating that sevelamer decreases LPS concentration, and its capacity to bind LPS and inhibit its inflammatory effect (Fig. 12) (41), we anticipate that sevelamer-induced reductions in plasma LPS concentration will lead to reduced inflammatory signaling (IKK/NF $\kappa$ B, MAPK, inflammatory genes) in muscle. Because sevelamer's effect is to reduce LPS, also we anticipate that flux through TLR4 (TLR4-MyD88 association) will be lower. In addition, we expect that the reductions in LPS concentration will predict (correlate with) changes (reductions) in TLR4 signaling and improved insulin signaling and sensitivity.

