**Interpretation and limitations.** We expect that the obese and T2DM subject will have an unfavorable intestinal microbiome profile (decreases in Bifidobacteria and Bacteroidetes) (54, 55) which will be associated with enhanced intestinal permeability and increased LPS level. Thus, we expect that these subjects will have an elevated inflammatory tone (TLR4 signaling) in muscle, which will reduce insulin action. Based upon previous animal studies (23-25), we anticipate that the synbiotic will restore gut epithelial integrity, decrease circulating LPS level, and ameliorate insulin resistance in obese and T2DM subjects. We also anticipate that sevelamer will decrease LPS concentration (36, 37) and will lead to reduced inflammatory signaling (IKK/NF $\kappa$ B, MAPK, inflammatory genes) in muscle. Because sevelamer's effect is to reduce LPS, also we anticipate that flux through TLR4 (TLR4-MyD88 association) will be lower. In addition, we expect that the reductions in LPS concentration will predict (correlate with) changes (reductions) in TLR4 signaling and improved insulin action.

Aim 1 will test whether a fat-rich diet alters the gut microbiome and disrupts the intestinal barrier in lean subjects resulting in increased LPS translocation. The goal of Aim 2 is different; in this Aim we are proposing a proof-of-principle experiment to evaluate whether modulating the microbiome and lowering plasma LPS improves insulin action in obese and T2DM subjects. We anticipate that modulating the microbiome and plasma LPS concentration will decrease inflammation and insulin resistance in these individuals. If these changes are the result of protection of gut barrier integrity from the increased fat intake which is common in obese and T2DM subjects, then sevelamer and the synbiotic also should prevent the inflammatory response and insulin resistance caused by the high fat diet in the lean subject from Aim 1. If the lean subjects are not protected from the high fat diet, but the obese and T2DM subjects benefit from sevelamer and the synbiotic, then improvements in inflammation and insulin action are likely caused by a mechanism different from protection against fat-induced damage. Other possible mechanisms by which LPS sequestration and/or microbiome modulation could improve inflammation and insulin action include changes in fructose-mediated endotoxemia (57), food energy extraction (9), appetite (10-13), bacterial flagellin levels (14), and peptidoglycans (15).

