TLR4 regulates numerous signaling cascades, including IKK/NF $\kappa$ B, JNK, ERK, p38 and SOCS. One or more branches downstream of TLR4 might be responsible for the negative effect of LPS on glucose metabolism. Dissecting the role of each of these branches in LPS-induced insulin resistance is beyond the scope of this grant application. Nonetheless, using our primary cell culture system and shRNA, in the future we could perform an in-depth analysis about the contribution of each of these signaling branches.

**Statistical analysis.** Experimental results will be expressed as means  $\pm$  SE. Comparisons of means between all the groups will be done by ANOVA for repeated measures (67). Associations between measures of LPS concentration vs. TLR4 signaling and vs. insulin signaling/sensitivity, within a group, will be determined by Pearson's correlation. For tests of correlation coefficients between groups we will use the Fisher's Z transformation (64). We will also determine the relationship between plasma LPS concentration vs. TLR4 signaling and LPS vs. insulin signaling/sensitivity, by using multiple regression analysis. Scatter plots will be done to look for outliers and to verify linearity. [name] is an experienced biostatistician who will direct the statistical analysis of this study. Based on our preliminary results and data from the literature (36, 65) regarding the variability of these measurements, we calculated that an  $n=12$  subjects/group is required to obtain power  $(1-\beta)$  of 0.80 with a 2-sided test at  $\alpha=0.05$  significance level. Assuming a  $\sim 20\%$  dropout rate, 15

subjects/group would be sufficient to achieve the required group sizes. The following data and power analysis (2-tailed) were obtained from an ongoing human study (PI: [name]).

Variable	Mean±SD Lean	N	Mean±SD Obese	n	Power
LPS Concentration	0.049±0.055	12	0.119±0.014	12	0.99
Insulin Sensitivity (M)	11.3±2.8	12	8.1±2.4	12	0.91
Ins Stim IRS1-P-Y	4.0±1.1	12	0.9±0.6	12	0.99
Variable	Mean±SD Lean	N	Mean±SD T2DM	n	Power
LPS Concentration	0.049±0.055	12	0.130±0.071	12	0.99
Insulin Sensitivity (M)	11.3±2.8	12	4.2±1.7	12	0.99
Ins Stim IRS-1 P-Y	4.0±1.1	12	1.5 ±1.0	12	0.99

For the following variables, data were obtained from published human studies (36, 40, 65).

Variable	Mean±SD Pre-Sevel	N	Mean±SD Post-Sevel	n	Power
LPS Concentration	3.6±3.0	12	1.2±2.3	12	0.99
CRP Concentration	4.8±2.4	12	0.44±0.24	12	0.99
Variable	Mean±SD Placebo	N	Mean±SD Synbiotic	n	Power

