**Metagenomics.** The metagenomics experiments will be carried out by [name] (Co-I), as described by his group (69-71). DNA is extracted using a kit from MoBio (Carlsbad, CA) and following the protocol established by the Human Microbiome Project Consortium (72). PCR-amplified 16S rDNA is sequenced using the Illumina HiSeq2000 platform, following the sequencing and data processing protocol designed by Caporaso (73). Taxonomy is assigned to each high-quality read based on the best matching Greengenes database sequence (74). Operational Taxonomic Units are clustered by using the QIIME toolkit (75). For Aim 1, ANOVA and t-test (and their non-parametric versions) and Chi-square/Fisher's exact test are applied to detect taxa with significantly different relative abundance either within the same individuals (*i.e.*, low fat vs. high fat) or between treatments (placebo, synbiotic, sevelamer). Shannon, UniFrac, and Bray-Curtis indices are compared to quantify the community-level variability among the samples within and between individuals. Multiple test corrections (*e.g.*, Benjamini-Hochberg-Yekutieli) are applied to control for false discovery rate. The response variable (microbial composition) is analyzed with the explanatory variables (insulin sensitivity, LPS level, etc.) to evaluate for associations by Generalized linear models. Models also are used for analyzing the influence of explanatory variables on the relative abundance of significantly changing bacterial taxa (or) communities with treatments. For Aim 2, the data analysis and comparisons between groups (obese, T2DM, and lean) and treatments (placebo, synbiotic, sevelamer) are done similarly as in Aim 1.

**Summary/Timetable.** We are very excited about this proposal which will study the role that the microbiome and endotoxemia play a key role in the pathogenesis of insulin resistance. The studies proposed are innovative because the role of the microbiome on insulin resistance is unclear and relevant because they could lead to the development of novel therapies for T2DM. This application describes a 3 year program:

Year 1: Start Aim 1      Year 2: Complete Aim 1; Start Aims 2 and 3      Year 3: Complete Aims 2 and 3

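### Aim 1 predicts a fall in Bifidobacteria, but the plan tests this taxon only inside an all-taxa false-discovery screen and states no power for any taxon

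*Combined protocol and SAP*

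**What the plan says.** In section D, Specific Aim 1, Interpretation and limitations, the plan expects the high fat diet to shift the flora and then names one taxon: "Specifically, we anticipate that there will be a reduction in Bifidobacteria content". The next steps rest on it. Bifidobacteria are said to protect the gut barrier, so permeability should rise and plasma LPS with it. The corresponding paragraph for Aim 2 expects "decreases in Bifidobacteria and Bacteroidetes" in obese and T2DM subjects.

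The tests are in Other specific methods, Metagenomics. ANOVA, t-tests, their non-parametric versions and Chi-square/Fisher tests "are applied to detect taxa with significantly different relative abundance either within the same individuals" or between treatments. Multiplicity is handled for the taxa together: "Benjamini-Hochberg-Yekutieli) are applied to control for false discovery rate". The named procedure is introduced only as an example. No taxon is set apart, and the number of taxa, the taxonomic rank and the false-discovery level are not given. Aim 2 is to be analysed in the same way.

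The only sizing statement is in Statistical analysis: 12 "subjects/group is required to obtain power" "of 0.80 with a 2-sided test at" the 0.05 level. Its supporting tables cover LPS, insulin sensitivity (M), IRS-1 phosphorylation, CRP, and MCP-1 and IL-6 mRNA. No microbiome variable appears in them.

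**The concern.** A false-discovery correction suits a search over many taxa. Here it also covers the one taxon that the Aim 1 hypothesis names in advance, so that taxon must clear a threshold that depends on how many others are tested and how many of them change. Because no power is given for any taxon, the reader cannot tell how strict that threshold is at this sample size.

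A non-significant corrected result for Bifidobacteria could therefore reflect the choice of correction family rather than the diet, and the first link of the mechanism would look weak for that reason. Leaving the matter open also invites an uncorrected Bifidobacteria test after the data are seen, which would carry little weight.

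**Working it through.** **The plan's own figure.** The sizing row nearest the 0.80 target is M, lean against obese: 11.3±2.8 and 8.1±2.4. The pooled SD is √((2.8² + 2.4²)/2) = √6.8 = 2.61, so d = 3.2/2.61 = 1.23. The noncentral t power for a two-sided 0.05 test is 0.78 with 11 per group and 0.82 with 12, which reproduces n=12. (The table prints 0.91 for this row; the difference does not affect this point.) Allowing for dropout, 12/(1 − 0.2) = 15, as stated. This sizing uses one unadjusted test and concerns no taxon.

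**Inputs for the taxon question.**
- From the documents: 12 completers per arm, 36 in the Aim 1 crossover, 36 per cohort in Aim 2.
- Assumed, because the documents are silent: false-discovery level q = 0.05; m = 20 to 200 taxa; independent taxa; 5-20% of taxa truly changed, all by the same amount; and a Bifidobacteria effect that gives exactly 0.80 in one two-sided 0.05 test at n=12.

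**Effect.** Paired power is the probability that a noncentral t variable with n−1 degrees of freedom and noncentrality dz·√n exceeds the two-sided critical value. Solving for 0.80 at n=12 gives dz = 0.89 (noncentrality 0.889 × √12 = 3.08). For 12 against 12 the corresponding value is d = 1.20.

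**Thresholds.** Benjamini-Hochberg rejects the k-th smallest p-value if it is at most k·q/m. Benjamini-Yekutieli replaces q by q/(1 + 1/2 + … + 1/m). If Bifidobacteria is the only rejection (k=1), paired power at n=12 and dz=0.89 is:

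| Taxa | Benjamini-Hochberg threshold | Power | Benjamini-Yekutieli threshold | Power |
|---|---|---|---|---|
| 50 | 0.05/50 = 0.001 | 0.18 | 0.001/4.50 = 0.00022 | 0.07 |
| 100 | 0.05/100 = 0.0005 | 0.12 | 0.0005/5.19 = 0.000096 | 0.04 |
| 200 | 0.05/200 = 0.00025 | 0.08 | 0.00025/5.88 = 0.000043 | 0.02 |

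**Full step-up procedure.** Other true changes relax the threshold, so the whole procedure was simulated, with 4,000 data sets per setting. Ranges cover 5-20% of taxa changed and are good to about 0.01-0.02. For the 12 placebo completers at dz=0.89:

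| Taxa | Benjamini-Hochberg | Benjamini-Yekutieli |
|---|---|---|
| 20 | 0.29-0.42 | 0.14-0.19 |
| 50 | 0.22-0.38 | 0.08-0.12 |
| 100 | 0.17-0.36 | 0.05-0.08 |
| 200 | 0.13-0.35 | 0.03-0.05 |

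A single unadjusted test has power 0.80 in each of these settings, by construction.

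**Sensitivity to the contrast, over 20-200 taxa.**
- Placebo plus sevelamer, n=24, dz=0.89: about 0.78-0.93 (Benjamini-Hochberg) and 0.51-0.81 (Benjamini-Yekutieli).
- All 36 crossover subjects, dz=0.89: 0.90-1.00 across both procedures.
- Aim 2 baseline, 36 against 36, d=1.20: 0.90-0.99 across both procedures.

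**Sensitivity to the effect.** With n=12 paired, 100 taxa and Bifidobacteria the only rejection, dz=1.5 gives 0.63 and 0.36, and dz=2.0 gives 0.93 and 0.76.

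**The case against.** The strongest reply is that the effect size is supplied by this review. The documents give no Bifidobacteria effect or SD, and most in vivo two-group effects in the sizing tables exceed d=1.20. For 12 against 12 with 20-100 taxa, d=1.74 keeps Benjamini-Hochberg power at 0.77-0.91 and Benjamini-Yekutieli power at 0.50-0.77; from d=2.38 upward they are at least 0.98 and 0.93. This stands: the loss is conditional, and its size cannot be derived from the plan.

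A second reply is that placebo only is the smallest sample available. All 36 subjects cross over, and the plan does not restrict the diet comparison to placebo. This stands in part. The synbiotic arm takes Bifidobacterium longum and oligofructose during both diets, so it cannot give a clean diet effect on this taxon. Placebo plus sevelamer is defensible, although it includes an active product. Moreover, the larger samples recover power only because dz is held at 0.89. At the effect that gives 0.80 in a single test with 36 subjects (dz=0.48), and with Bifidobacteria the only rejection among 10 to 200 taxa, power again falls to 0.47-0.15 and 0.32-0.06.

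Third, Benjamini-Yekutieli is the stricter reading of what the plan offers as an example. This is fair, so both procedures are reported; in the placebo arm the loss is substantial under either.

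Fourth, nothing in the plan says that a non-significant taxon would be taken to refute the mechanism. Permeability and LPS are measured directly, and community indices and generalized linear models are also planned. This is also fair: misreading is a risk, not something the plan commits to.

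**Conclusion.** The point holds as a cheap improvement. The taxon on which the Aim 1 mechanism starts has no pre-specified test of its own and no power statement. In the placebo arm, the contrast free of both study products, the planned correction could cut power from 0.80 to about 0.13-0.42 (Benjamini-Hochberg) or 0.03-0.19 (Benjamini-Yekutieli). That rests on dz=0.89, q=0.05, and 20-200 independent taxa of which 5-20% change equally. Real relative abundances are correlated, so these figures are illustrative.

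Three stronger readings are tempting, and the documents support none of them.
- A reader might infer that the trial misses a stated power of 0.80 for Bifidobacteria. That figure belongs to LPS, insulin sensitivity, signalling and inflammation measures; no taxon was sized.
- A reader might infer that the Aim 2 prediction for obese and T2DM subjects is underpowered too. At d=1.20 with 36 per cohort, power stays at 0.90 or above.
- A reader might infer that the plan makes only one taxon prediction. That is true of the diet effect in Aim 1, but Aim 2 also names Bacteroidetes.

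**What to change.** In the Metagenomics paragraph:

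- **Aim 1:** pre-specify Bifidobacterium relative abundance as the single confirmatory taxon, tested at two-sided 0.05 outside the false-discovery family, as the paired low against high fat comparison in the placebo arm. Give placebo plus sevelamer as a supporting analysis.
- **Aim 2:** for consistency, test Bifidobacterium at baseline, lean against obese/T2DM, written as one contrast, with Bacteroidetes second in fixed order.
- **All other taxa:** keep the false-discovery correction, state the procedure, its level and the taxonomic rank, and label the results exploratory.

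The stool samples are already scheduled (day 24 of each diet in Aim 1, before treatment in Aim 2), so no new data are needed. The cost is a few lines of text and one extra 0.05-level test per aim outside the false-discovery family. No taxon outside these pre-specified tests could then be presented as confirmatory.

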#### 4. MANUSCRIPTS: N/A
